4.1.1.1. Electronic Participant-Reported Outcomes (ePROs)

There are two types of missing data for ePRO measures: missing data at the 'form' level and missing data at the 'item' level. Form level missing refers to a participant missing an entire PRO assessment for a given time point (e.g. a given day for the HFDD and a given week for the PROMIS SD SF 8b). In general, form level data may be missing due to participant's early withdrawal from the study, the inability to evaluate an endpoint at a particular time point, or non-compliance. By design of the eDiary, there will be no item level missing data for the respective ePRO questionnaires because the participants have to select an answer for an item in order to move on to the next item on the eDiary/electronic handheld device. This does not apply to the MENQOL (see below).

4.1.1.1.1. Hot Flash Daily Diary (HFDD)

Participants' assessments of HF will be collected at the timepoints indicated in the SoA and recorded electronically twice daily using the sponsor developed HFDD.

A diary day for the calculation of the frequency and severity of HF consists of the evening entry (Evening Hot Flash eDiary) and the morning entry (Morning Hot Flash eDiary) of the

version 3.0 Page: 22 of 87

subsequent day. A day will be considered available for the calculation of the frequency and severity of HF, if at least the evening or the morning entry (of the subsequent day) is not missing. The daily number of hot flashes will be calculated as the sum of hot flashes documented in both the evening and morning diary. Retrospective data entry is possible for a limited time. For the morning diary these retrospective entries will be allowed on the same day between 11:00AM and 11:59PM. For the evening diary the retrospective entry option will be available between midnight until 10:59AM on the day after the missed entry. If only the evening or morning entry is available, then only this will be used for that particular day.

For the evaluation of the frequency and severity of HF, the daily HF assessments will be aggregated to a mean daily frequency and a mean daily severity HF score from the data of a particular week (see Section 4.1.2.1). In case data is missing for more than 2 days within a week, the value for that particular week will be set to missing. Further details regarding imputation rules in case of missing week values are described in Section 4.2.1.

4.1.1.2. Patient-reported Outcomes Measurement Information System Sleep Disturbance Short Form 8b (PROMIS SD SF 8b)

The PROMIS SD SF 8b will be filled out by the participants using the eDiary. All PROMIS SD SF 8b items must be answered to produce a valid total score. Handling of missing weekly assessments is described in Section 4.3.1.2.

4.1.1.1.3. Menopause Specific Quality of Life Scale (MENQOL)

The MENQOL will be filled out by the participants using the eDiary at the timepoints indicated in the SoA.

For the MENOOL, participants have the option to skip single questions (e.g. if they do not feel comfortable to complete them). Missing item score will be imputed, if the participant has responded to more than one half of the domain items (i.e. at least two items in the vasomotor domain, two items in the sexual domain, four items in the psychosocial domain and nine items in the physical domain of the MENOOL). The imputed score is calculated from values converted for analysis according to scoring table (Table 6-2) and rounded to a whole number. The imputed value is the mean for that item generated from the other subjects who responded as follows: For missing item score at baseline, all subjects who responded to the item are considered. For post-randomization, only the responses of the participants in the same treatment group are used. When data from other participants will be used for imputation half of the participants within a treatment group must have responded to the item before an imputed value can be calculated. If the participant answered 'yes' but did not indicate 'how bothered' she was (partially missing data), the value is imputed from her own answers by calculating the mean of her 'bothered' scores for all her 'yes' answers within that domain. If she answered 'no' to all other domain items, the imputed score would be generated from the mean of all the subjects who responded 'yes' to the same item as discussed above (Lewis, 2004). If missing item scores within a domain cannot be imputed (because participant responded to half or less than half of the domain items), the domain score will be set to missing and the total score will be calculated as the mean of the remaining available domains.

Further details of scoring and handling of missing weekly assessments are described in Section 6.1.3, and Section 4.3.1.

version 3.0 Page: 23 of 87

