- **H1-** H_{01} : $\mu_{1P} \le \mu_{1V}$ versus H_{11} : $\mu_{1P} > \mu_{1V}$ where μ_{1P} and μ_{1V} stand for the mean change from baseline in the placebo (P) and verum (V) group in HF frequency at week 4.
- **H2-** H_{02} : $\mu_{2P} \le \mu_{2V}$ versus H_{12} : $\mu_{2P} > \mu_{2V}$ where μ_{2P} and μ_{2V} stand for the mean change from baseline in the placebo (P) and verum (V) group in HF frequency at week 12.

The hypotheses for the key secondary efficacy endpoints are defined as:

- **H3-** H_{03} : $\mu_{3P} \le \mu_{3V}$ versus H_{13} : $\mu_{3P} > \mu_{3V}$ where μ_{3P} and μ_{3V} stand for the mean change from baseline in the placebo (P) and verum (V) group in PROMIS SD SF 8b total score at week 12.
- **H4-** H_{04} : $\mu_{4P} \le \mu_{4V}$ versus H_{14} : $\mu_{4P} > \mu_{4V}$ where μ_{4P} and μ_{4V} stand for the mean change from baseline in the placebo (P) and verum (V) group in MENQOL total score at week 12.

For the confirmatory efficacy analysis, a hierarchical testing approach will be applied, involving the two primary efficacy variables and the two key secondary variables.

The type I error rate will be controlled at a one-sided α =0.025 level. For a positive study outcome, both tests for primary variables need to be significant.

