4.1.2. Data Rules

Definition of baseline: The latest available valid measurement excluding unscheduled measurements at or before the start of treatment (for treated subjects) / randomization date (for randomized but not treated subjects). If the last observation available prior to randomization is the measurement from the Screening Visit, this would be used as the baseline value. In case a wash-out period was necessary, measurements taken during the prescreening visit will not be used as a baseline value unless specified otherwise.

Change from baseline: To calculate the absolute change from baseline the baseline value will be subtracted from the value under treatment/follow-up, i.e.,

Absolute change = post baseline value – baseline value.

Some parameters will be additionally analyzed as relative change defined as

Relative change = 100 * [(post baseline value – baseline value) / baseline value].

Derivation of intercurrent event (ICE): Intercurrent events that occurred from randomization date (for randomized but not treated subjects) / start of treatment (for treated subjects) to day 84 inclusive will be flagged.

version 3.0 Page: 24 of 87

For the "permanent discontinuation of randomized drug", "intake of prohibited medication having impact on efficacy" and "interruption/ discontinuation in intake of adjuvant endocrine therapy", if the ICE occurs on or before the 5th day of the week, it will be flagged for the respective week. If the ICE occurs on the 6th or 7th day of the week, it will be flagged from the following week. For example, if the participant permanently discontinues from the randomized drug on the 2nd day of week 4, the ICE will be flagged from week 4 onwards. If the discontinuation from the randomized drug occurs on the 6th day of week 4, then the ICE will be flagged from week 5 onwards. For the ICEs "intake of prohibited medication having impact on efficacy" and "interruption/ discontinuation in intake of adjuvant endocrine therapy", if the end date for the impact on efficacy occurs on the 1st or 2nd day of the week, the respective week should not be flagged. If the end date of impact on efficacy occurs on or after the 3rd day of the week, the week should be flagged.

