4.3.1.3. Sensitivity Analyses

The sensitivity analysis similar to described in Section 4.2.2 will be performed for key secondary endpoints.

For tipping point analysis, the adjustments will be applied with the following delta values:

- PROMIS SD SF 8b total T-score, delta values of 3, 6, 9, etc.
- MENQOL total score, delta values of 0.5, 1, 1.5, etc.

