6.1.3. MENQOL

The MENQOL questionnaire is comprised of 29 items assessing the presence of menopausal symptoms and the impact of menopause on health-related quality of life over the past week (Hilditch et al. 2008). For each item, the participant indicates if they have experienced the symptom (yes/no). If they select "yes", they rate how bothered they were by the symptom using a six-point verbal descriptor scale, with response options ranging from 0 'not at all bothered' to 6 'extremely bothered'. The conversion table is provided in Table 6–2.

version 3.0 Page: 63 of 87

Table 6-2: MENQOL - conversion table

Subject Response	Converted Score
The participant responded 'NO', she did not experience the problem	1
The participant experienced the problem and rated it as '0' on the bothered scale;	2
The participant experienced the problem and rated it as '1' on the bothered scale;	3
The participant experienced the problem and rated it as '2' on the bothered scale;	4
The participant experienced the problem and rated it as '3' on the bothered scale;	5
The participant experienced the problem and rated it as '4' on the bothered scale;	6
The participant experienced the problem and rated it as '5' on the bothered scale;	7
The participant experienced the problem and rated it as '6' on the bothered scale;	8

Domain scores are calculated by averaging the converted individual item scores (range 1-8) related to the respective domain. (Domains: Vasomotor - items 1 to 3, Psychosocial – items 4 to 10, Physical- items 11- to 26, Sexual – items 27 to 29.) For a MENQOL total score the aggregated mean of the mean domain scores is calculated. Higher scores indicate greater bother. MENQOL total score, domain scores and individual item scores will be summarized in this study.

In this study the MENQOL will be applied electronically and responded to by the participants at home and during selected in person visits at weeks 1 (i.e. baseline), 4, 8, 12, 16, 26, 36, 52 and 56 (i.e. Follow-up).

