6.3. Appendix 3: Tipping point analysis

A tipping point analysis will be applied by applying an unfavorable additive shift (referred to as delta adjustment) to values imputed to fill in the missing and unobservable data that occur in presence of ICEs. Delta adjustment will be applied only to imputed values in the elinzanetant arm. No delta adjustment will be applied to missing values that occur outside of the time frame of any ICE. The following steps will be implemented for primary endpoint, i.e., frequency of HF:

- 1. The imputation step will be done as described in Section 4.2.1.
- 2. Prior to the analysis step, each imputed value in the elinzanetant arm that occurs in the time frame of an ICE would have a value of "delta" added to it (see Section 4.2.2 for settings of delta for each type of endpoint). The same value of delta will be applied at each time point.
- 3. Observed, imputed, and adjusted data will be analyzed and results combined as described in Section 4.2.1.
- 4. The steps for imputation, modeling, combining the results will be repeated with increasing settings of "delta" (see Section 4.2.1) for each primary endpoint until the estimated treatment difference at Week 4 or Week 12 is no longer statistically significant at the 0.025 one-sided level. The corresponding "delta" setting will be selected as the tipping point for that endpoint.

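### Should H4 be re-analysed because the MENQOL total averages whichever domains can be scored, which may differ between baseline and Week 12?

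*SAP*

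**What the plan says.** SAP 4.1.1.1 says that the device forces an answer to every item, with MENQOL as the exception. SAP 4.1.1.1.3 then works in two steps.

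- **Item level.** A missing item is imputed if more than half of its domain is answered: "at least two items in the vasomotor domain, two items in the sexual domain, four items in the psychosocial domain", and nine in the physical domain. A symptom marked as present without a bother rating is filled from the participant's other ratings in that domain.
- **Domain level.** If half or fewer of the items are answered, "the domain score will be set to missing and the total score will be calculated as the mean of the remaining available domains".

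SAP 6.1.3 defines the total as the mean of the four domain means, each on a 1 to 8 scale. Two domains have only three items: vasomotor (items 1 to 3) and sexual ("Sexual – items 27 to 29"). Change is defined in SAP 4.1.2 as "Absolute change = post baseline value – baseline value", with no condition on which domains enter either value. Protocol 9.4.3 refers the scoring to the questionnaire guidelines.

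For H4, SAP 4.3.1.3 says: "The sensitivity analysis similar to described in Section 4.2.2 will be performed for key secondary endpoints". That means the normality check with rank ANCOVA, and the tipping point. SAP 4.3.1.4 adds the two supplementary estimands.

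**The concern.** Two blank answers out of 29, if both fall in the vasomotor or the sexual domain, remove a quarter of the total's weight and raise each remaining domain from 1/4 to 1/3. If this happens at one visit only, the change score mixes symptom change with a change of composition. If it happens at both visits, the treatment effect is re-weighted towards the remaining domains.

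The planned robustness analyses do not reach this. A total from three domains counts as observed, so multiple imputation leaves it alone. In the tipping-point analysis (SAP 6.3), "Delta adjustment will be applied only to imputed values in the elinzanetant arm". The rank ANCOVA takes totals as scored, and the supplementary estimands alter the handling of intercurrent events but not the scoring. The two SAP supplements concern safety. At stake is the credibility of an alpha-controlled quality-of-life claim.

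**Working it through.** **Inputs from the documents** (SAP Section 5, Table 5–1): 243 and 122 evaluable, SD 1.00, difference 0.4, one-sided alpha 0.025, stated power 94.90%. An exact two-sample t calculation gives 94.90%, so the plan's figure is reproduced.

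**Assumptions.** The documents give no skip rates, domain means or domain effects. All such values below are assumed and shown as ranges.

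**1. When a domain is lost.** From the item thresholds in SAP 4.1.1.1.3, loss needs at least 2 of 3 vasomotor or sexual items blank, 4 of 7 psychosocial, or 8 of 16 physical. A single blank is normally imputed and the domain is kept.

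**2. One participant, no true change, one domain lost at Week 12 only.**
Shift = (mean of the other three domains − lost domain) / 4.
- Gap of 1 point: 0.25. Gap of 2: 0.50. Gap of 4: 1.00.
- Domains 7, 4, 4, 1: total 16/4 = 4.00; without the last, 15/3 = 5.00; shift +1.00.
- Domains 6, 4, 4, 7: total 21/4 = 5.25; without the last, 14/3 = 4.67; shift −0.58.

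**3. Bias from unequal skipping.** Shift in the treatment difference = (arm difference in one-visit loss) × gap/4. For a shift of 0.04 (10% of 0.4):
- gap 1: 0.04/0.25 = 16 percentage points
- gap 2: 0.04/0.50 = 8 points
- gap 4: 0.04/1.00 = 4 points

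A shift of 0.04 would raise the one-sided false-positive rate from 2.5% to 5.5% if it favoured elinzanetant, or lower power to 89.9% if it did not.

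**4. Re-weighting under equal skipping.** Let a share p of both arms lose the same domain, with p from 0.02 to 0.15.
- Vasomotor-only effect of −2: four-domain effect −2/4 = −0.50; without the sexual domain −2/3 = −0.667. Inflation is p × (0.667/0.50 − 1) = p/3, or 0.7% to 5.0%. Without the vasomotor domain the effect is 0, so dilution is p, or 2% to 15%.
- Effects −2, −0.6, −0.6, −0.4: four-domain −3.6/4 = −0.90; without sexual −3.2/3 = −1.067, inflation 0.4% to 2.8%; without vasomotor −1.6/3 = −0.533, dilution 0.8% to 6.1%.

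With no drug effect, equal skipping creates no difference.

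**5. Noise.** An artefact with SD s in a share p gives a total SD of √(1 + p·s²).
- p = 0.02, s = 0.25: SD 1.0006, power 94.9%.
- p = 0.15, s = 0.5: √1.0375 = 1.0186, power 94.2%.

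**6. What extra analyses would add.** A simulation used 400 trials of 243 and 122, baseline domain means 6, 4, 4, 4, a vasomotor-only effect giving a true total effect of −0.50, and 15% random loss of the sexual domain.

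| Loss | Planned scoring | Same domains at both visits | All four domains (complete cases) |
|---|---|---|---|
| Week 12 only | −0.525 | −0.526 | −0.500 |
| Both visits | −0.523 | −0.523 | −0.497 |

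Under this equal skipping, matching domains returns practically the planned estimate. Requiring all four removes the re-weighting but gives up data. If 2% to 15% always skip a domain, 365 × 0.02 = 7 to 365 × 0.15 = 55 women would leave the analysis, and power would be 94.6% (238 and 120) to 91.3% (207 and 104).

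**The case for a change.** The strongest case for a change is that H4 is a confirmatory test, skipping is permitted by design, and the treatment of the two key secondary endpoints is uneven: for PROMIS SD SF 8b, SAP 4.1.1.2 requires every item for a valid total. The domain summaries in SAP 4.4.3 show gaps by arm and week but do not pair baseline with Week 12. Under SAP 4.1.2, descriptive tables also omit data after premature discontinuation from the treatment week, although those data enter the model. Nor do the documents settle whether the rule comes from the questionnaire guideline, since the reference cited in SAP 4.1.1.1.3 stands before the available-domain sentence.

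These points are accurate, and it stands that no planned analysis re-estimates H4 under another scoring. They do not show that the dependence would be invisible. SAP 4.1 puts relevant derived variables in the subject listings, and SAP 4.1.1 puts all missing or partial diary data there, so participants with changed composition can be identified. Nor do the points show a better scoring. The four-domain version would replace collected answers with imputed ones, against the treatment-policy strategy of SAP 4.2.1. Unequal skipping is the one route to a material false-positive rate, and the documents give no ground for expecting it. Domain losses at baseline precede treatment and are balanced in expectation by randomization.

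**Conclusion.** No change is needed. The rule is a fair trade-off: it keeps collected answers at the cost of some inconsistency in composition. Item-level imputation confines domain loss to questionnaires with half or more of a domain blank. On the assumed ranges, power stays at or above 94.2%, and equal loss of the sexual domain moves the effect by at most 5.0%. The larger dilution of up to 15% would need 15% of women in a hot-flash trial to leave most vasomotor items blank, together with an effect confined to that domain. Arm bias of 0.04 needs a 4 to 16 point difference in one-visit loss.

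The consequence is also bounded: H4 is last in the fixed sequence, and SAP Section 2 ties success to H1 and H2: "For a positive study outcome, both tests for primary variables need to be significant". The conclusion rests on assumed skip rates and gaps. If the listings showed many totals resting on fewer than four domains, or clearly more in one arm, an analyst could count them by arm and visit and add a domain-matched check, labelled post hoc if treatment codes were already open. That is ordinary reporting practice and does not require the plan to be amended.

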4.1.1.1.4. Beck Depression Inventory (BDI-II)

The BDI-II will be filled out by the participants using the eDiary at the timepoints indicated in the SoA. No imputation of missing assessments will be performed.

4.1.1.1.5. Insomnia Severity Index (ISI)

The ISI will be filled out by the participants using the eDiary at the timepoints indicated in the SoA. No imputation of missing assessments will be performed.

4.1.1.1.6. European Quality of Life 5-dimension 5-level questionnaire (EQ-5D-5L)

The EQ-5D-5L will be filled out by the participants using the eDiary at the timepoints indicated in the SoA. No imputation of missing assessments will be performed.

4.1.1.1.7. Short Form-36 Health Survey Acute (SF-36 acute)

The SF-36 acute will be filled out by the participants using the eDiary at the timepoints indicated in the SoA. Transformed and calculated scores are provided by external Vendor based on SF-36 manual.

4.1.1.1.8. Sleepiness scale

The Sleepiness Scale will be assessed together with the HFDD evening diary at bedtime at the timepoints indicated in the SoA. It consists of three items asking the participant to rate the degree of sleepiness felt in the morning (item 1), afternoon (item 2) and evening (item 3).

Missing item level responses will not be imputed, the average of item scores will be used to create a daily sleepiness score. A 7-day average score can be derived if a daily sleepiness score is available for at least 5 out of 7 of days, otherwise the 7-day average score will be set as missing. The baseline value will be calculated by aggregating all available days during the 14 days prior to start of treatment to a mean daily sleepiness. A minimum of 11 days should be available for the derivation of the baseline value.

4.1.2. Data Rules

Definition of baseline: The latest available valid measurement excluding unscheduled measurements at or before the start of treatment (for treated subjects) / randomization date (for randomized but not treated subjects). If the last observation available prior to randomization is the measurement from the Screening Visit, this would be used as the baseline value. In case a wash-out period was necessary, measurements taken during the prescreening visit will not be used as a baseline value unless specified otherwise.

Change from baseline: To calculate the absolute change from baseline the baseline value will be subtracted from the value under treatment/follow-up, i.e.,

Absolute change = post baseline value – baseline value.

Some parameters will be additionally analyzed as relative change defined as

Relative change = 100 * [(post baseline value – baseline value) / baseline value].

Derivation of intercurrent event (ICE): Intercurrent events that occurred from randomization date (for randomized but not treated subjects) / start of treatment (for treated subjects) to day 84 inclusive will be flagged.

version 3.0 Page: 24 of 87

For the "permanent discontinuation of randomized drug", "intake of prohibited medication having impact on efficacy" and "interruption/ discontinuation in intake of adjuvant endocrine therapy", if the ICE occurs on or before the 5th day of the week, it will be flagged for the respective week. If the ICE occurs on the 6th or 7th day of the week, it will be flagged from the following week. For example, if the participant permanently discontinues from the randomized drug on the 2nd day of week 4, the ICE will be flagged from week 4 onwards. If the discontinuation from the randomized drug occurs on the 6th day of week 4, then the ICE will be flagged from week 5 onwards. For the ICEs "intake of prohibited medication having impact on efficacy" and "interruption/ discontinuation in intake of adjuvant endocrine therapy", if the end date for the impact on efficacy occurs on the 1st or 2nd day of the week, the respective week should not be flagged. If the end date of impact on efficacy occurs on or after the 3rd day of the week, the week should be flagged.

The "permanent discontinuation of randomized drug" ICE will be flagged for participants who were randomized but not treated. These participants have an event at randomization for the Kaplan-Meier analysis on the time from randomization (for randomized but not treated subjects) / start of treatment (for treated subjects) to the first occurrence of the intercurrent event "Permanent discontinuation of randomized treatment". For the main analytical approach, the missing post-baseline data will be imputed as described in Section 4.2.1.

End-of-treatment ePRO assessments after premature treatment discontinuation:

Patient-Reported Outcome assessments (PROMIS SD SF 8b, MenQoL, EQ-5D-5L, BDI-II, ISI and SF-36 acute) are scheduled to occur during the following days:

Questionnaires	Assessment Week	Completion days* (inclusive)
PROMIS SD SF 8b, EQ-5D-5L	1	8-9
PROMIS SD SF 8b, EQ-5D-5L	2	15-16
PROMIS SD SF 8b, EQ-5D-5L	3	22-23
PROMIS SD SF 8b, EQ-5D-5L, MenQoL, ISI, BDI-II	4	29-30
PROMIS SD SF 8b, EQ-5D-5L, MenQoL, ISI, BDI-II	8	55-57
PROMIS SD SF 8b, EQ-5D-5L, MenQoL, ISI, BDI-II, SF-36 acute	12	83-85

^{*}Completion days are referring to days from randomization.

First, scheduled assessments during the completion days will be assigned to the respective week.

Only in case no scheduled assessment is available for a particular week, assessments done at EoT, unscheduled timepoints or follow-up (in this order of priority) will be used, and they will be mapped to the next available, protocol-planned assessment week as described below.

- If the assessment occurs during the completion days as above, it will be assigned to the respective week.
- Up to and including Week 3 (only PROMIS SD SF 8b and EQ-5D-5L): If the EoT/ follow-up/ unscheduled assessment is on 5th day of the week or later, then the assessment will be mapped to the respective week (i.e., assessments on Days 6-7* will

version 3.0 Page: 25 of 87

be mapped to Week 1, Days 12-14 to Week 2 and Days 19-21 to Week 3). Otherwise, no mapping will occur, and the respective week will be considered missing. If multiple assessments are available within a particular week, the last assessment (i.e., the one closest to the scheduled assessment) will be used for mapping.

- From Week 4 onwards: a 2-week window will be used to map the available assessments to Week 4 (Days 15-28), Week 8 (Days 43-54*), or Week 12 (71-82*). A similar 2-week window will be used from Week 16 to Week 52. Within each 2-week-window, the last available assessment (i.e., the one closest to the scheduled assessment) will be used for mapping.
 - *Week 1 = Days 2-8; Day 8 (week 1), Days 55/56 (week 8) and Days 83/84 (week 12) are scheduled assessments, and no mapping would be required, therefore, these days are not considered in the window for mapping.
- In case an assessment is assigned to Week 2 or 3 and to Week 4, based on the above rules, it will be shown for Week 2 or 3 in the descriptive tables. The Week 4 assessment will only be used in the model-based analyses.
- Assessments from follow-up visits will be shown as follow-up in the descriptive tables, and the value mapped to a specific treatment week will only be used in the model-based analyses.
- In the descriptive tables, data collected after premature discontinuation of treatment will not be shown for the respective treatment week. Assessments occurring up to 2 days after discontinuation (inclusive) will still be considered under treatment and shown for the respective week. Out of the assessment collected post treatment discontinuation (+ 2 days), the one closest to the planned time point of follow-up (i.e. discontinuation date + 28 days) will be shown as follow-up assessment. In case two assessments are equally close to that date, the first one will be selected.

Laboratory values <X or >X: For laboratory values lower than a limit of detection X which are given as **<**X , half the value of X will be used for analysis (i.e., values reported as "**<**X", "**<**X.X", "**<**X.XX" or etc. the value for analysis used will be derived by "X/2", "X.X/2", "X.XX/2" etc). Differences between 2 values **<**X will be assigned values of 0. Ratios between 2 values **<**X will be assigned a value of 1. For values which are higher than a limit of detection Y, given as Y, the value of Y will be used for analysis.

Repeated measurements at the same visit after start of treatment: If more than one post-randomization measurement is available for a given visit, the first available observation will be used in the data summaries and all observations will be presented in the data listings.

Start of treatment refers to the first drug intake and will be identified based on the eCRF entry.

Time to event: The randomization date (for randomized but not treated subjects) /start of study treatment (for treated subjects) will be used as the start date for the calculation of time to event. Therefore, the time of event will be defined as "date of event – randomization date (for randomized but not treated subjects) / start of study treatment (for treated subjects) +1".

Unscheduled Assessments: Extra assessments (e.g. laboratory data or vital signs) associated with non-protocol visits will be included in listings, but not in the summary tables or figures, unless specified otherwise.

version 3.0 Page: 26 of 87

Definition of phases: The following phase definitions are used for displaying treatment duration, compliance, exposure and adverse events. The two phases in the Part A of the study represent the approximately first 12 weeks of the study, in which participants receive either placebo or elinzanetant 120mg and the approximately 14 weeks when all participants receive elinzanetant (i.e. the participants in the placebo arm will switch to elinzanetant). The start and end date of the phases is defined as following:

- Phase 1 (Part A):
 - Start date = start of treatment for treated subjects / randomization date for subjects, randomized, but not treated
 - \circ End date = first day of phase 2 study drug intake 1 day (based on the eCRF entry)

(For participants who stayed in the study for at least 12 weeks and received the phase 2 study drug);

OR

(For participants who have not received the drug phase 2 due to early discontinuation of randomized treatment or study withdrawal)

Week 12 assessment date or the post treatment phase end date, whichever is earlier

(this is for participants who discontinued from study drug but agreed to complete the assessments until Week 12)

or

Study drug discontinuation date or EoT assessment date, whichever is later (For participants who discontinued from randomized study drug before receiving phase 2 study drug and decided to go to the follow up period or withdraw from the study).

Note: HFDD morning diary and PRO questionnaires which were completed one day after the phase 1 end date will be assigned to phase 1. For participants who were randomized but not treated, the end date = randomization date.

- Phase 2 (Part A):
 - Start date = first day of phase 2 study drug intake (identified based on the eCRF entry)
 - End date = Visit T9 date (For participants who completed the phase 2/Part A, i.e. 26 weeks)
 or

Study drug discontinuation date or EoT assessment date, whichever is later (*For participants who discontinue from treatment/study prematurely during the second phase*).

Note: HFDD morning diary and PRO questionnaires which were completed one day after the phase 2 end date will be assigned to phase 2.

In addition, Part B and Part C of the study will be defined as Phases 3 and 4 in the following way:

• Phase 3 (Part B):

version 3.0 Page: 27 of 87

- Start date = Visit T9 date +1
- End date = Visit T13 date (For participants who completed the phase 3/Part B, i.e. 52 weeks) or

Study drug discontinuation date or EoT assessment date, whichever is later (For participants who discontinue from treatment/study prematurely during the third phase).

• Phase 4 (Part C):

- Start date = Visit T13 +1 (i.e. start day of Part C) drug intake (identified based on the eCRF entry)
- End date = end of treatment period date (For participants who completed the phase 4, i.e.
 Part C)

or

Study drug discontinuation date or EoT Part C assessment date, whichever is later (For participants who discontinue from treatment/study prematurely during the Part C).

